Trial Centre	NIHR Wellcome Trust Clinical Research Facility, Southampton University Hospital NHS Foundation Trust, [name]
Trial Sponsor	RHM MED1354
Code	
Design	Phase II prospective controlled human Neisseria lactamica infection study
Population	Healthy volunteers aged 18-45 years
Sample size	Total up to 44 volunteers Group 1: Nasal inoculation with Neisseria lactamica with eradication on day 4 – up to 22 volunteers or until 11 colonised on day 4 Group 2: Nasal inoculation with Neisseria lactamica with eradication on day 14 – up to 22 volunteers or until 11 colonised on day 4
Follow up duration	Group 1: Challenge at day 0, eradication on day 4, follow up on days 5, 14 and 32 Group 2: Challenge at day 0, follow up on day 4 and 7, eradication on day 14, follow up on day 15, 24 and 42
Planned Trial Period	13/03/2017– 30/9/2018
Primary Objective	To compare the effect of short (4 days) versus longer (14 days) oropharyngeal carriage on systemic and mucosal humoral immunogenicity following nasal inoculation with Neisseria lactamica
Secondary Objective	To assess the efficacy of oral Ciprofloxacin in eradicating nasal Neisseria lactamica colonisation by 24 hours after treatment
Microbial challenge material	Neisseria lactamica Wild type – dose 100000 (10^5) cfu

2. Abbreviations

AE	Adverse Event
ALP	Alkaline Phosphatase
ALS	Advanced Life Support
ALT	Alanine transaminase
AR	Adverse Reaction
cfu	Colony Forming Unit
CRF	Case Report File
DSUR	Development Safety Update Report
ESC	External Safety Committee
GCP	Good Clinical Practice
GP	General Practitioner
HRA	Health Research Authority
ICH	International Conference on Harmonisation
ILS	Immediate Life Support
MHRA	Medicine and Healthcare products Regulatory Agency
NHS	National Health Service
NIHR	National Institute for Health Research
NIHR-WTCRF	NIHR Wellcome Trust Clinical Research Facility
Nlac	Neisseria lactamica
PBS	Phosphate Buffered Saline
PCR	Polymerase Chain Reaction
QA	Quality assurance
RBC/HPF:	Red blood cell per high power field
REC	Research Ethics Committee
SAE	Serious Adverse Event

SAR	Serious Adverse Reaction
SmPC	Summaries of Product Characteristics
SOP	Standard Operating Procedure
SUSAR	Serious Unexpected Serious Adverse reaction
TOPS	The Over-volunteering Prevention System
UAR	Unexpected Adverse Reaction
UHS NHS FT	University Hospital Southampton NHS Foundation Trust

3. Background and rationale

3.1 Vaccines and immunity to carriage

Childhood glycoconjugate vaccines (e.g. meningococcal, pneumococcal and *Haemophilus*) have been shown to be highly effective due to both their direct effect on the immunity of the individual and also as a result of herd protection. This herd protection is a result of vaccine-induced modification of colonisation reducing inter-host transmission. Future successful vaccines will target pathogen colonisation, using antigens known to induce immunity critical for colonisation, in age groups most likely to transmit to others. The most direct and effective way to measure carriage reduction by vaccines is by inducing carriage of a defined organism expressing antigens of interest (experimental human challenge) in persons exposed to vaccine and measuring the subsequent carriage of the bacterium.

3.2 Immunity in natural carriage

Colonisation by bacteria is an immunising event; we proved this in humans by inoculating university students intranasally with the harmless commensal *N. lactamica* and we observed both specific systemic and mucosal antibody responses by 4 weeks (Evans, Pratt et al. 2011). Likewise a human challenge model has been used to study responses to pneumococci in which, in addition to humoral responses, T cell responses were induced by asymptomatic carriage of wild-type *S. pneumoniae*, with an increase in IL-17A+ Th cells in both the blood and bronchoalveolar lavage fluid by 21-56 days post challenge, suggesting that similar to animal models of carriage, Th17-mediated responses are also mobilised in humans (Wright, Bangert et al. 2013). Assessment of the breadth of cellular responses to bacterial carriage suggests that unlike humoral responses, they are not restricted to the most immunodominant antigens (Davenport, Guthrie et al. 2003) (Glennie, Banda et al. 2012). However, repeated colonisation by the same species is known to occur throughout the lifetime of humans (Bidmos, Neal et al. 2011). Experimental challenge with defined bacteria could tease out the mechanisms of this, which include waning of immunity over time, the induction of an incorrectly polarised T cell response, lack of cross-reactivity between strains or active immune evasion mechanisms employed by bacteria to subvert host immune effector mechanisms.

3.3 *Neisseria lactamica*

Neisseria lactamica is a non-pathogenic lactose-fermenting Gram-negative diplococcus, frequently found in the nasopharynx, particularly in young children. Transmission occurs through close contact and only a few cases of clinical significance have been reported (Denning and Gill 1991) (Brown, Ragge et al. 1987) (Lauer and Fisher 1976). Although *N. lactamica* and *N. meningitidis*, colonise the same location within the upper respiratory tract, previous studies suggest they engage with the human mucosal immune system in very different ways (Vaughan, Gorringe et al. 2009). In contrast to *N. meningitidis*, *N. lactamica* maintains a commensal relationship with the host in the absence of an adaptive immune response. *N. lactamica* lacks a polysaccharide capsule, so any adaptive immune responses to this bacterium must be directed at non-capsular antigens, providing a good platform for assessing non-anti-polysaccharide immunity against colonising bacteria when compared with wild type *N. lactamica*.

3.4 *Neisseria lactamica* for human challenge

N. lactamica (Nlac) has been shown to be safe in human challenge as we have found in over 340 volunteers experimentally inoculated with this organism (Evans, Pratt et al. 2011) (Deasy, Guccione et al. 2015). Even at a very low dose of 10^4 colony forming units (cfu), long lasting colonisation with Nlac is easily induced in 35-65% of participants. We showed (Evans, Pratt 2011) that increasing the inoculum to 10^5 cfu increased the subsequent carriage of *N. lactamica* to 50%. In 80-90% of those successfully colonised, this is detectable by 1-2 weeks. Data regarding earlier detection of colonisation is currently lacking. (Evans, Pratt et al. 2011) (Deasy, Guccione et al. 2015) Colonisation has a clear effect on the nasal mucosal microbiome, in that meningococcal acquisition is effectively inhibited in participants who carry the organism (Deasy, Guccione et al. 2015). Colonisation is immunogenic with an increase in specific serum IgG by 2 weeks and specific salivary IgA by 4 weeks (Evans, Pratt et al. 2011). No eradication therapy has previously been given following experimental inoculation but Ciprofloxacin has been shown to be effective in the eradication of *N. meningitidis* with clearance in 100% of previously colonised individuals after 24 hours. (Pugsley, Dworzack et al. 1987) To design future planned studies using *N. lactamica* nasal inoculation and colonisation in order to prevent invasive *N. meningitidis* disease, it is necessary to further evaluate the colonisation kinetics and efficacy of eradication following antibiotic treatment. Planned studies include infection with *N. lactamica* engineered to express antigens included in modern vaccines such as NadA and PorA. Such studies will require containment of volunteers and for ethical and economic reasons it will be necessary to make the period of colonisation as short as possible, and to eradicate carriage of the organism at the end of the experiment. Previous challenges we have done with *N. lactamica* have allowed the volunteers for prolonged periods of follow-up over 6 months.

3.5 General overview

This study will compare the effect of short (4 days) versus longer (14 days) periods of nasal carriage of *N. lactamica* on immunogenicity and confirm the efficacy of oral eradication therapy with ciprofloxacin. Healthy adult volunteers will receive a nasal inoculation of *N. lactamica* and eradication therapy will be given on day 4 or 14. This information will be used to inform the design of future research into the colonisation kinetics and immunogenicity of related organisms. Specifically, the Medical Research Council has funded us to inoculate humans with genetically modified *N. lactamica*. Before designing the protocols for that study we need to know whether a short containment of the volunteers will be sufficient for immunogenicity, and how quickly we can discharge the volunteers after ciprofloxacin eradication. A wild-type strain of *N. lactamica* Y92-100 will be used for this study, selected because we have previously used it safely in experimental challenge of over 340 human volunteers. The same strain is the parent strain for the GMO work described above.

4. Objectives

4.1 Primary objective

- To compare the effect of short (4 days) versus longer (14 days) oropharyngeal carriage on systemic and mucosal humoral immunogenicity following nasal inoculation with *Neisseria lactamica*

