5.1 Overview

This is a prospective controlled human challenge study in which participants will be inoculated intranasally with *N. lactamica* and eradication therapy will be given at day 4 or day 14. Colonisation will be assessed at day 4 for both groups and day 7 and 14 for group 2. Efficacy of eradication will be checked 1 day and 10 days after eradication therapy is given (day 5 and day 14 for group 1, day 15 and day 24 for group 2) and immunogenicity will be assessed at day 14 post inoculation and day 28 post eradication.

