6.6 The optimal and safe dose of the inoculum

Based on the previous *N. lactamica* work it is estimated that 50% of volunteers will be colonised 1-2 weeks after inoculation with 10^5 cfu without any safety concerns (Deasy, Guccione et al. 2015). The hypothesis is that those who are colonised at day 4 will exhibit seroconversion by day 14, confirming biologically 'significant' colonisation.

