13.1 Endpoints of the study

Primary endpoint

- Rise in serological specific antibody titre comparing day 0 versus day 14 and 28 days post eradication and comparing early (day 4) versus late (day 14) eradication

Secondary endpoints:

- Assessment of colonisation – culture of *N. lactamica* from throat swabs at day 4 for group 1 and days 4, 7 and 14 for group 2
- Assessment of eradication – culture of *N. lactamica* from throat swabs on the day of eradication, one day, 10 days and 28 days after eradication
- Rise in mucosal specific antibody titre comparing day of screening versus day 14 and 28 days post eradication and comparing early (day 4) versus late (day 14) eradication
- Change in nasal cytokine profile comparing day 0 versus day 4, 14 and 28 days post eradication and comparing early (day 4) versus late (day 14) eradication
- Difference in environmental shedding between short (group 1) and longer (group 2) periods of colonisation.

Safety endpoints:

- Occurrence of unsolicited adverse events within the study period
- Occurrence of serious adverse events within the study period

Safety analysis will be carried out for all volunteers that received the inoculum, regardless of whether or not they complete the study.

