13.2 Sample size

The previous experimental *N. lactamica* challenge study showed a significant rise in serological antibody titre against *N. lactamica* over 2 weeks (Deasy, Guccione et al. 2015). This gave SDs on a log-10 scale of 0.11 for IgA saliva and 0.26 for serum total IgG. For this study, using the SD of 0.26 we will be able to confirm a 4 fold rise with 10 carriers of *N. lactamica* with 90% power using analysis of variance.

Allowing for a drop out rate of approximately 10%, we will therefore recruit volunteers until we have 11 individuals colonised for each group up to a maximum of 22 volunteers for each group. At a dose of 10^4 colony forming units (cfu), long lasting colonisation with *N. lactamica* is easily induced in 35-65% of participants. We showed that increasing the inoculum to 10^5 cfu increased the subsequent carriage of *N. lactamica* to 50% (Evans, Pratt 2011). Therefore approximately 44 individuals will be enrolled. Assuming a screening failure rate of 5%, we will need to screen approximately 46 potential participants to achieve colonisation in 11 of each group.

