13.3 Statistical analysis

Statistical analysis will be performed by the study team and [name], Public Health England, Colindale. Differences between groups at each time point will be assessed using Fisher exact test and between time points within groups by McNemar test.

14. Study quality and Management procedures

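### The primary endpoint leaves out the mucosal half of the primary objective and does not make the early v late contrast decisive, and the sample size is stated for a rise, not for that contrast

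*Combined protocol and SAP*

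**What the plan says.** Section 4.1, repeated in the synopsis, sets one primary objective: short against longer carriage, judged "on systemic and mucosal humoral immunogenicity following nasal inoculation with" *N. lactamica*. The only secondary objective (4.2) concerns ciprofloxacin eradication.

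Section 13.1 gives the primary endpoint as "Rise in serological specific antibody titre comparing day 0 versus day 14 and 28 days post eradication", and adds "and comparing early (day 4) versus late (day 14) eradication". Mucosal antibody appears only among the secondary endpoints, as "Rise in mucosal specific antibody titre comparing day of screening versus day 14 and 28 days post eradication", followed by its own early v late comparison.

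Section 13.2 takes log10 SDs of "0.11 for IgA saliva and 0.26 for serum total IgG" from an earlier challenge study. It states that 10 carriers give 90% power to confirm a 4-fold rise by analysis of variance. It derives nothing from the saliva SD.

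Section 13.3 says "Differences between groups at each time point will be assessed using Fisher exact test and between time points within groups by McNemar test". No section gives a significance level, an order of testing or a success criterion. The one stated hypothesis, in 6.6, is that "those who are colonised at day 4 will exhibit seroconversion by day 14".

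**The concern.** The objective is a comparison between groups on two compartments. The endpoint covers one compartment and mixes two kinds of question: whether antibody rises within a group, and whether the groups differ. Section 13.3 provides for both kinds of test and ranks neither. The sample size and the hypothesis in 6.6 both concern a rise.

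A report could therefore say that the primary endpoint was met because titres rose in each group, with no evidence on what shortening carriage from 14 to 4 days costs. Section 3.5 says the result will inform whether a short containment is enough for immunogenicity in the planned study of genetically modified *N. lactamica*. A rise in group 1 bears on that, but it does not show how much response is lost relative to 14 days, which is what 4.1 asks.

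**Working it through.** **Inputs.** From 13.2: SD 0.26 (serum IgG) and 0.11 (saliva IgA) on the log10 scale, 10 carriers, 90% power, 4-fold rise (log10 4 = 0.602). The plan applies the 10 per group (11 colonised each after dropout). From 5.1: "immunogenicity will be assessed at day 14 post inoculation and day 28 post eradication". Assumed: two-sided 5%, because no level is stated. Section 13.2 does not say whether an SD is that of a change or of a level at one visit, so both are carried. The SD of a change between two uncorrelated visits is SD × √2, which gives 0.26 × 1.414 = 0.368 for serum and 0.11 × 1.414 = 0.156 for saliva.

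**The plan's own figure.** Power for a 4-fold effect, from the noncentral t distribution:

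| Reading | Power |
|---|---|
| Between groups, 10 per group, SD 0.26 | 99.8% |
| Between groups, 10 per group, SD 0.368 | 93.3% |
| Between groups, 10 in total (5 + 5), SD 0.26 | 89.2% |
| Within one group, 10 paired, SD 0.26 | above 99.9% |
| Within one group, 10 paired, SD 0.368 | 99.5% |

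The stated 90% is not reproduced with 10 per group and SD 0.26. Two unstated readings come close to it. The figure is under-specified, but not too small for a 4-fold effect.

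**What 13.2 would say for the between-group contrast.** For a two-sample t test with 10 per group (18 degrees of freedom) and 90% power, the standardised difference is d = 1.534. Detectable fold difference = 10^(d × SD).

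- Serum, SD of change 0.26: 1.534 × 0.26 = 0.399, or 2.50-fold.
- Serum, SD of change 0.368: 1.534 × 0.368 = 0.564, or 3.66-fold.
- Saliva IgA, SD 0.11: 1.534 × 0.11 = 0.169, or 1.47-fold.
- Saliva IgA, SD 0.156: 1.534 × 0.156 = 0.239, or 1.73-fold.

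Power for a 2-fold serum difference is 69% with SD 0.26 and 41% with SD 0.368.

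**Can the endpoint be met without a group difference?** A simulation took 10 per group, a per-visit SD of 0.26, visit correlations of 0, 0.5 and 0.8, and 50,000 runs each. Both groups were given the same true 4-fold rise at both later visits, and t tests on log10 changes were used at 5% each. At least one within-group test was significant in about 100% of runs. At least one of the two early v late tests was significant in about 9%, which is simply their combined false-positive rate. In about 91% of runs there was a significant rise and no significant group difference.

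**Timing.** Day 14 is the same time since inoculation in both groups. Twenty-eight days after eradication is day 32 in group 1 and day 42 in group 2 (10.1). Day 14 is therefore the only post-challenge blood visit matched on time since inoculation.

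**The case against.** A reader might infer that the objective can be claimed without ever being tested. The documents do not support that. The early v late comparison is written into the serum endpoint and the mucosal endpoint in 13.1, and 13.3 plans between-group tests at each time point. What is missing is priority, not the comparison.

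A reader might also count six primary tests (two rises in each of two groups, plus two between-group tests) and cite a 26% familywise error. The count is inferred: the plan states no number, and pooling the groups for the rise gives four. The 26% is 1 − 0.95^6 under independence, and simulation with the actual dependence gives about 20%. Nor can the rises be expected true effects and sources of false positives at once. For the two early v late tests alone, the figure is 9% to 10%.

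The near-certainty of a within-group rise is conditional. It supposes that the rise occurs after only 4 days of carriage, which is unknown because section 3.4 says eradication has not been given before in this model. It also rests on t tests. Under exact McNemar with 10 pairs, at least 6 converters and no reversals are needed (p = 2 × 0.5^6 = 0.031). With a true 4-fold rise and SD 0.26, assumed responder cut-offs of 2-, 3- and 4-fold give power of 99.6%, 82% and 38%. The plan defines no cut-off. This objection stands, but it shows a further gap and does not remove the first one.

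Finally, the rises are informative in themselves for the future study. That also stands, so they should be kept as supportive results.

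**Conclusion.** The point holds as a mismatch of objective, endpoint and sample size. The primary endpoint omits the mucosal part of 4.1, the mucosal endpoint answers to no objective in 4.2, and no rule prevents a within-group rise from being reported as success on a between-group question. It does not hold as a claim that the comparison is left untested.

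On the contrast that the objective needs, 10 per group detects 2.5-fold (up to 3.7-fold) in serum IgG and 1.5- to 1.7-fold in saliva IgA at 90% power. These figures assume a two-sided 5% level, log-normal titres and 10 evaluable carriers per group. The range reflects what 13.2 leaves unsaid about its SDs; the upper ends suppose uncorrelated visits. The mismatch itself does not depend on these figures. The plan should be changed, but no design element has to move.

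**What to change.** 1. **13.1 and 13.3.** Make the early v late difference in change of log10 serum specific IgG from day 0 the single primary contrast. Day 14 is the natural time because of the matching shown above. Analyse it as a continuous outcome with a confidence interval, since Fisher and McNemar need a yes/no outcome.
2. **13.1.** Label the within-group rises and the 28-day post-eradication comparison as supportive. The latter should stay, because day 14 is also group 2's eradication day and cannot show any later response to longer carriage.
3. **4.1, 4.2 and 13.1.** Move the mucosal comparison to a secondary objective. Report it with a confidence interval at both visits and do not make it conditional on the serum result. Section 3.4 reports salivary IgA rising by 4 weeks, against 2 weeks for serum IgG, so day 14 alone may be early. Name the baseline by sample: tables 10.1 and 10.2 take nasal wash at screening but saliva from day 0.
4. **13.2.** State the significance level, say what each SD describes, and give the detectable between-group differences set out above beside the 4-fold rise.

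The cost is wording only; no visit, sample or volunteer is added. The stated sensitivity becomes less favourable. Because volunteers can state a preference for a group (5.3), the contrast stays non-randomised and should be described so wherever it is reported.

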4.2 Secondary objectives

- To assess the efficacy of oral ciprofloxacin in eradicating nasal *Neisseria lactamica* colonisation by 24 hours after treatment

5. Description and justification of the study design

5.1 Overview

This is a prospective controlled human challenge study in which participants will be inoculated intranasally with *N. lactamica* and eradication therapy will be given at day 4 or day 14. Colonisation will be assessed at day 4 for both groups and day 7 and 14 for group 2. Efficacy of eradication will be checked 1 day and 10 days after eradication therapy is given (day 5 and day 14 for group 1, day 15 and day 24 for group 2) and immunogenicity will be assessed at day 14 post inoculation and day 28 post eradication.

5.2 Study volunteers

Healthy volunteers aged 18-45 years will be recruited and challenged until 11 volunteers in each group are colonised with *N. lactamica* at day 4 or up to a maximum of 44 volunteers in total. Based on our previous studies with *N. lactamica*, colonisation was achieved in 35% of *N. lactamica* -inoculated non-smokers at a dose of 10^4 cfu, (Deasy, Guccione et al. 2015) and increasing the inoculum to 10^5 cfu increased the subsequent carriage of *N. lactamica* to 50% (Evans, Pratt 2011). Therefore inoculating up to 44 participants will result in approximately 22 colonised individuals.

5.3 Randomisation and blinding

There will be no randomisation or blinding in this study. Prior to enrolment volunteers can give their preference for early eradication at day 4, or late eradication at day 14. Once one group has reached 22 volunteers, any remaining volunteers will be recruited in the other group to ensure both arms include a maximum of 22 participants.

5.4 Challenge procedure

Our priority is to conduct this study without causing harm to the volunteer. As *N. lactamica* is a non-virulent commensal organism and based on previous challenge studies with this organism, we consider that the likelihood of disease resulting from inoculation of the volunteers is extremely low.

5.5 Duration of volunteer participation

The duration of involvement of volunteers in the study will be 32 days (group 1) or 42 days (group 2) from enrolment.

